#### 3.1 Inclusion Criteria

- All participants must have signed an informed consent document indicating they understand the purpose of the study and the procedures required for the study and are willing to participate by complying with the study procedures and restrictions.
- 2. Male or female individuals of any race; between 18 to 60 years of age, inclusive.
- 3. Resides in a stable living situation, according to the investigator's judgment.
- 4. Diagnosis of bipolar disorder I or II for at least 1 year in duration, as established by the SCID-I, and verified with medical records and/or confirmation of diagnosis by treating clinician. Patients will be in a nonacute phase at the time of initial screening and have been so for at least 1 month.
- 5. No more than moderate clinical symptom burden severity, as defined by the following:
  - Montgomery Asberg Depression Rating Scale ≤ 20
  - Young Mania Rating Scale ≤12
- 6. Individuals medically stable enough to complete an 8 week clinical trial, in the judgment of the investigator

- 7. Women of childbearing potential must have a negative pregnancy serum test at screening, negative pregnancy urine test at baseline, and agree to use adequate protection (i.e. double barrier method) for birth control.
- 8. Antidepressant (AD) medications are allowed if the subject has been treated with a stable dose for at least 2 months before screening.
- 9. Individuals receiving a single mood stabilizer (e.g., lithium. valproate, or lamictal) are allowed if a stable dose has been maintained for at least 2 months prior to screening.
- 10. Individuals may be receiving one treatment of each the following groups: antidepressants, mood stabilizers, and atypical antipsychotics other than clozapine, but not more than one from each group.
- 11. Individuals taking ripseridone, lurasidone, or ziprasidone must be currently taking solder: doses of 3mg, 40mg, and, 80mg, respectively.
- 12. Subjects may be treated with inclusionary antipsychotic drugs as long as they are on a stable dose of injectable medication for 2 months or a sable dose of an oral medication for 1 month. Exclusionary antipsychotic drugs are listed in Appendix 2.
- 13. Patients with a history of compliance with a drug treatment regimen for bipolar disorder, as noted in medical/psychiatric history.

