#### 9.4.11 Adverse Event (AE) Monitoring

The PI or a designee (eg, a licensed, qualified medical practitioner such as a physician's assistant or a nurse practitioner) listed on the site delegation of authority log must assess the severity and relationship to study medication(s) of all AEs. All observed or volunteered AEs regardless of treatment group or

suspected causal relationship to the investigational product(s) will be recorded on the AE page(s) of the electronic database.

For all AEs, the investigator must pursue and obtain information adequate both to determine the outcome of the AE and to assess whether it meets the criteria for classification as an SAE requiring immediate notification to the Sponsor or its designated representative.

For all AEs, sufficient information should be obtained by the investigator to determine the causality of the AE. The investigator is required to assess causality and indicate that assessment on the source document and electronic database. For AEs with a causal relationship to the investigational product, follow-up by the investigator is required until the event or its sequelae resolve or stabilize at a level acceptable to the investigator.

Adverse events (serious and non-serious) should be recorded on the source document and electronic medical record from the date the informed consent form (ICF) was signed until the end of their participation in the study, ie, the subject has discontinued or completed the study.

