#### 9.5.2 Columbia Suicide Severity Rating Scale

The C-SSRS was developed by a team of researchers at Columbia University to address the need for standardized classification of suicide reports to assess suicide risk. This scale consists of a baseline evaluation that assesses the lifetime experience of the subject with suicide events and suicidal ideation and a post-baseline evaluation that focuses on suicidality since the last study visit. A baseline C-SSRS will be completed at the screening visit. The C-SSRS Since Last Visit form will be completed at all subsequent visits and telephone calls (Day 21, Day 35, and Day 49).

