Data Analysis Plan for Northwestern- Janssen R&D Collaboration Study

Protocol Title: Testing the ability of JNJ-18038683, a selective serotonin (5-HT)7 antagonist, to

improve cognition and reduce residual depressive symptoms in stable bipolar patients

Protocol Identifier Number: 18038683BCD2001

Northwestern University IRB Number: STU00200919-MOD0042

Version: 1.13

Date: 08.04.2021

Goals:

The goals of this study are to evaluate the efficacy of JNJ-18038683 in an 8-week trial to ameliorate the cognitive deficit and reduce residual depressive symptoms in 60 stable bipolar outpatients receiving treatment for depression. JNJ-18038683 will be studied and compared with placebo as adjunctive treatment to standard pharmacologic treatment for bipolar disorder. Sixty patients will be enrolled and randomized with a 1:1 ratio to one dose of JNJ-18038683 or placebo providing 30 subjects for each treatment arm. The initial intention was to follow stratified randomization based on the presence/absence of atypical APDs with 5-HT7 antagonism so that there is a balance in the assignment of active treatment and placebo in individuals who are and are not, receiving atypical APDs with 5-HT7 antagonism. However, due to recruitment difficulties, the stratified randomization method was not able to be followed as anticipated and was amended.

Assessments and Events:

Demographics, medical history, physical examination, serum pregnancy test, urine drug test, SCID-I diagnosis, and screening neurocognitive assessments will be done only during the screening visit. Urine pregnancy testing is performed at the baseline visit.

Table 1: Assessments completed during the screening visit only

Event /Assessment	Screen
Medical History & Demographics	X
Physical Examination	X
Serum Pregnancy Test	X
Urine Drug Screen	X
Inclusion/Exclusion Criteria	X
SCID-I	X
Screening neurocognitive assessments	X

Neurocognitive battery will be the primary measure of interest and evaluated at baseline and 8 weeks. The clinical global severity scores (CGI-BP), Young Mania Rating (YMRS), Scale for Tardive Dyskinesia (AIMS), Montgomery Asberg Depression Rating Scale (MADRS), Electrocardiogram and Clinical Safety Laboratory Tests will be collected at screening or baseline, and at 4 and 8 weeks. A measure of functional ability (SLOF) also will be assessed at baseline and 8 weeks. The schedule of these assessments is listed in table 2.

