Table 2: Assessments completed during the screen visits/baseline visits and at week 4 and/or week 8

Event/Assessment	Screen	Day 1*	Day 28	Day 56
Electrocardiogram	Х		X	Х
Clinical Safety Laboratory Tests	Х		X	Х
Montgomery Asberg Depression Rating Scale		Х	Х	Х
SLOF		Х		Х
AIMS		Х	Х	Х
Screening neurocognitive assessment	Х			
Neurocognitive Assessments Cleveland Battery		Х		Х
CGI-BP		Х	Х	Х
Young Mania Rating Scale		Х	Х	Х

^{*}Day 1 is equal to Baseline

Vital signs, C-SSRS (suicide tendency), concomitant medication, and adverse events experienced by patients will be collected during study visits at screening, baseline, and at weeks 1, 2,4, 6, and 8. In addition, data will be collected at weeks 3, 5, 7, and 12 via phone calls for C-SSRS (suicide tendency), concomitant medication, and adverse events.

Table 3: Assessments completed during the screen visits/baseline visits and at weeks 1,2,4,6 and 8

Event/Assessment	Screen	Day 1	Day 7	Day 14	Day 28	Day 42	Day 56
Vital Signs	Х	Х	Х	Х	Х	Х	Х
C-SSRS*	Х	Х	Х	Х	Х	Х	Х
Assessment of Concomitant	Х	Х	Х	Х	Х	Х	Χ
Medication*							
Assessment of Adverse Events*	Х	Х	Х	Х	Х	Х	Х

^{*} assessments will also be collected at 21, 35, 49 and 84 days via phone calls.

Statistical Analysis:

Screening data and drop out data:

Screen assessments listed in table 1 will be summarized for all the patients including reasons for screen failures. Concomitant medications were the reasons for most screen failures and will be documented. Included patients will be compared with excluded patients based on appropriate statistical methods (parametric or non-parametric) for the variables in table 1. During the study period, all dropouts and reasons for drop out will be tabulated.

In this blinded RCT, individuals with bipolar disorder received active drug (JNJ-18038683) or a placebo after screening and the completion of baseline assessments. Subjects in the two treatment arms will be compared on all the baseline efficacy measures, measures of psychopathology related to bipolar disorder, e.g., YMRS, MADRS, CGI-BP, SLOF measures, demographic variables, and suicide status.

Primary analysis for efficacy:

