Secondary analyses related to efficacy:

The secondary analyses regarding change in verbal fluency test scores will include identification of patients in each arm who improved in verbal fluency scores. The analysis plan includes exploring the effect of concomitant meds, gender or race that might contribute to treatment response. For this purpose, improvement in verbal fluency can be grouped as a dichotomous response and used as a dependent variable in a logistic regression model. The usual method of grouping will be improvement of ≥0.5 SD from the baseline scores. Using this model, the odds of improvement in verbal fluency can be compared in the active treatment group against the placebo group. In this model, the variables, age, gender, lab values and presence/absence of concomitant meds, baseline MADRS total score, YMRS and Clinical Global Severity score mania or depression severity may influence performance on cognitive testing and will be tested as potential covariates using one or few covariates at a time due to sample size restrictions.

Additional secondary analyses will study the effect of treatment group on other cognitive and behavioral measures including: 1) Digital Symbol Task, 2) Brown-Peterson Consonant Trigram Memory Task, 3) WISC-III Mazes; 4) Wisconsin Card Sorting Test; 5) MADRS total score,6) YMRS, and 7) Clinical Global Severity score using a mixed model repeated measure ANCOVA as described above. If indicated, variables such as age, gender, concomitant meds, will be examined, as will be done for the primary outcome measure.

Adverse Events:

A tabular summary of all anticipated and unanticipated serious or non-serious adverse events will be presented, including drop-outs due to any side effects or safety reasons. For each serious or other adverse events, the summary includes the adverse event term, affected organ system, number of participants at risk, and number of participants affected, by the study arm or comparison group. Using appropriate parametric or non-parametric methods, each type of adverse event will be compared between groups. All adverse events, e.g. development of suicidal ideation or behaviors or switch to mania/hypomania, will be examined thoroughly for impact on primary and secondary outcome measures. We will assess group differences, excluding subjects without these two side effects.

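### By-arm counts of suicidality and manic switch rest on adverse-event reporting alone, because post-baseline C-SSRS has no planned analysis and switch has no scale-based definition

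*SAP*

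**What the plan says.** **C-SSRS.** Protocol section 9.1 lists it as an outcome measure. Section 9.5.2 gives a baseline form at screening, covering lifetime experience, and then: "The C-SSRS Since Last Visit form will be completed at all subsequent visits and telephone calls". The SAP (Assessments and Events) agrees. The C-SSRS, with other safety items, "will be collected during study visits at screening, baseline, and at weeks 1, 2,4, 6, and 8", and by telephone at weeks 3, 5, 7 and 12. In the SAP's analysis text, suicide status appears only among the variables compared between arms at baseline.

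**YMRS.** The SAP places it among the scales that "will be collected at screening or baseline, and at 4 and 8 weeks". Entry requires "Young Mania Rating Scale ≤12" (Protocol 3.1). The SAP compares it by treatment group as a secondary outcome: "6) YMRS, and 7) Clinical Global Severity score using a mixed model repeated measure ANCOVA as described above". It is also a candidate covariate for the cognitive outcomes. No YMRS value or change is named as a switch to mania or hypomania.

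**Adverse events.** Protocol 9.4.11 records "All observed or volunteered AEs regardless of treatment group" or suspected cause. For each adverse-event term, the SAP will show participants at risk and participants affected by arm, and will compare each type between groups. It then says: "All adverse events, e.g. development of suicidal ideation or behaviors or switch to mania/hypomania, will be examined thoroughly". That sentence goes on to make their impact on the primary and secondary outcomes the object of the examination. The section closes by saying that group differences will be assessed after leaving out participants who did not have these two side effects.

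**The concern.** The drug is being tested partly for an antidepressant effect, as an add-on in bipolar disorder, and the SAP itself singles out suicidality and switch. The trial asks every patient about suicidality with a structured instrument at each contact and rates mania twice on treatment. A reader of the results would expect the by-arm frequency of each harm to come from those instruments. Under the SAP it comes from adverse-event reports.

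A scale gives the same question to every patient at the same times, with a known denominator. An adverse-event report needs someone to decide that a response amounts to an event. Without a rule for that decision, the count depends on individual judgement at two sites, and the report could not say how many positive scale responses lie behind it. The closing sentence adds a separate problem, because it appears to define a comparison restricted to patients who had the events.

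**Working it through.** **1. What the scales provide.** From the Protocol's Schedule of Assessments (section 7.0 and Appendix 1) and SAP Tables 2 and 3:
- C-SSRS: screening, Day 1, and Days 7, 14, 21, 28, 35, 42, 49, 56 and 84. That is 11 contacts, 9 of them after Day 1.
- YMRS: Days 1, 28 and 56, so 2 ratings after Day 1.
- With 60 patients and full follow-up: 9 × 60 = 540 C-SSRS assessments and 2 × 60 = 120 YMRS ratings after Day 1. These figures describe available data. They do not measure bias.

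**2. What the SAP does with them.**

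| Harm | Scale after Day 1 | Planned scale analysis | Source of by-arm count |
|---|---|---|---|
| Suicidality | C-SSRS, 9 contacts | None named | Adverse-event table |
| Manic switch | YMRS, Days 28 and 56 | Score in mixed model; covariate | Adverse-event table |

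Neither document says when a C-SSRS response or YMRS value must be entered as an adverse event.

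**3. Why the YMRS model does not supply a count.** A mean does not identify how many patients switched. With assumed values in an arm of 30, two patients rising 15 points shift the mean by (2 × 15)/30 = 1.0. Thirty patients rising 1 point each shift it by (30 × 1)/30 = 1.0. The model sees the same shift in both cases. Also, the SAP's primary-analysis text pairs its mixed model with last value carried forward, and the secondary model refers back to it. On that reading, a patient who leaves before Day 28 without a final rating contributes the Day 1 YMRS. A switch in that patient could then be seen only through an adverse-event report, so scale and report need to be read together.

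**4. The closing sentence.** Suppose, for illustration, that 4 of 30 patients on active drug and 1 of 30 on placebo have one of the events. After removing patients without them, the proportions are 4/4 and 1/1, equal by construction. Any other outcome would be compared between 4 and 1 patients selected by something that happened after randomisation. If the sentence is a slip and patients with the events are meant to be left out, it becomes a sensitivity analysis of efficacy. On neither reading does it yield an incidence by arm.

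**5. What a scale-based count could show at 30 per arm.** The documents state no figure for either harm, so there is none to reproduce.
- Upper limit for 0/30, two-sided exact 95%: 1 − 0.025^(1/30) = 0.116, or 11.6%. One-sided: 1 − 0.05^(1/30) = 0.095, or 9.5%.
- Fisher exact two-sided p: 5/30 versus 0/30 gives 2 × C(30,5)/C(60,5) = 2 × 142,506/5,461,512 = 0.052. For 6/30 versus 0/30 it is 2 × C(30,6)/C(60,6) = 2 × 593,775/50,063,860 = 0.024.

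A contrast below 6 versus 0 would not reach 0.05, so the table should be descriptive.

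**The case against.** The strongest reply is that the SAP already covers this ground. It promises participants affected by arm for every adverse-event term and a between-group comparison of each type. YMRS is compared by arm as a secondary outcome, and so is the Clinical Global Severity score; the CGI-BP severity rating has a mania component (Protocol 9.4.6). Adverse events are assessed at every contact where the C-SSRS is given, the Protocol's definition of an adverse event is broad (9.3.5.1), and ideation disclosed to a rater can count as observed. Much of this stands, and it rules out three stronger readings that a reader might infer:

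- **That there will be no by-arm count, or that both harms enter only as adverse events.** The adverse-event table is a by-arm count, YMRS scores are compared by arm, and suicide status is compared at baseline. What is missing is a count taken from the scales.
- **That adverse-event reporting will under-count, or differ between sites.** The documents show only that no conversion rule exists. Under-counting is possible but not demonstrated. Nor can the 1.0-point YMRS shift above be called small, since no YMRS standard deviation or distribution is given.
- **That YMRS above 12 can serve as the definition of switch.** Twelve is an entry limit. A move from 12 to 13 would qualify, no change from Day 1 would be required, and the YMRS is first scheduled on Day 1 although eligibility is marked at screening.

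The reply does not supply a use for the post-baseline C-SSRS, a definition of switch, or a sound reading of the closing sentence.

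**Conclusion.** The point holds as a gap in the safety analysis. Nine scheduled post-baseline C-SSRS contacts per patient have no planned output, switch has no scale-based definition, and frequencies of the two harms the SAP names rest on adverse-event reporting with no rule tying it to the scales. The closing sentence of the Adverse Events section, taken literally, discards the randomised denominator. The effect on the final counts cannot be sized from the documents, because no event rates or reporting completeness are given. The gain is in consistency of ascertainment and a clear denominator, not in power: with 30 per arm and full follow-up, zero events would still be compatible with a rate of up to 11.6%. This is a cheap improvement; it does not affect the primary efficacy analysis.

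**What to change.** Before unblinding, add to the SAP one table by arm showing n/N over all randomised patients with post-baseline data, with exact 95% confidence intervals, labelled descriptive:

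1. **Suicidality.** Any suicidal ideation, and separately any suicidal behaviour, on the C-SSRS Since Last Visit forms from Day 7 to Day 84. Show these by baseline status. The screening form covers lifetime experience, so counting only responses that are new or worse than screening could lose recurrence in patients with a past history.
2. **Manic switch.** A YMRS-defined switch at Day 28 or Day 56, using a threshold or a change from Day 1 that the sponsor prespecifies, shown next to reported switch adverse events.
3. **Reconciliation.** List scale-positive patients without a matching adverse event, and the reverse.
4. **Closing sentence.** Reword it so that the comparison of these two harms keeps the randomised denominator. If an efficacy sensitivity analysis was meant, state that separately and say which patients it leaves out.

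The cost is two derived variables, one table and a few lines of SAP text. No new assessments are needed. The drawback is low precision at 30 per arm, which the table should state.

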#### 3.2 Exclusion Criteria

- 1. Failure to perform screening or baseline examinations
- 2. Hospitalization within 8 weeks before screening, or change in mood stabilizing or antidepressant medication or dose within 2 months prior to screening
- 3. Individuals who have participated in another clinical study within the past 2 months.
- 4. Individuals with tardive dyskinesia.
- 5. Individuals with other DSM-V Axis I or Axis II primary diagnoses.

- 6. Diagnosis of alcohol or substance use disorder within the past 3 months.
- 7. Subject assessed to be at significant suicide risk based on responses to the Columbia Suicide Severity Rating Scale (C-SSRS).
- 8. History of myocardial infarction, unstable angina, uncontrolled hypotension or hypertension within 3 months before screening.
- 9. Clinically significant abnormality on screening ECG.
- 10. Alanine transaminase (ALT) or aspartate transaminase (AST) > 2.5 times the upper limit of normal (ULN).
- 11. History of stroke, brain tumor, head trauma with loss of consciousness, or other clinically significant neurological condition within 12 months before screening.
- 12. Individuals with other uncontrolled medical conditions, in the opinion of the investigator.
- 13. Use of drugs known to be metabolized by CYP2D6 (see Appendix 2)

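### One supplementary adverse-event analysis in the SAP is miswritten: it keeps only the patients who developed suicidality or a manic/hypomanic switch

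*SAP*

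**What the plan says.** The last paragraph of the SAP (Adverse Events) contains three separate plans.

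1. A table of adverse events with numbers at risk and affected by arm, after which "each type of adverse event will be compared between groups". No exclusion is attached.
2. A look at consequences for efficacy: adverse events, with the examples "development of suicidal ideation or behaviors or switch to mania/hypomania, will be examined thoroughly for impact on primary and secondary outcome measures".
3. The closing sentence: "We will assess group differences, excluding subjects without these two side effects".

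The two side effects in the third plan are the two examples in the second. Nothing else in the SAP or the protocol corrects, defines or reverses the sentence.

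The SAP's opening section sets the randomised sample at 60, with "placebo providing 30 subjects for each treatment arm". Events are recorded at all visits to week 8, and the SAP adds that "data will be collected at weeks 3, 5, 7, and 12 via phone calls for C-SSRS (suicide tendency), concomitant medication, and adverse events". Recording therefore continues to day 84, four weeks after the week 8 (day 56) efficacy assessment.

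**The concern.** Excluding subjects *without* the events leaves only subjects *with* them. Both events are described as developing during the study, so the retained group is defined after randomisation. It is also likely to be small, because the protocol screens against both risks at entry. Section 3.2 excludes a "Subject assessed to be at significant suicide risk based on responses to the" C-SSRS, and Section 3.1 requires "Young Mania Rating Scale ≤12".

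At stake is the answer to a sensible question: whether these two psychiatric events disturb the treatment comparison on cognition and mood. The literal rule cannot answer it. Reversing one word gives the complementary set of patients, so two analysts could report quite different results and both cite this sentence. If the reading is settled only after unblinding, results could influence the choice.

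The sentence also leaves open whether one event or both are needed, over what period an event counts, and whether the result is a sensitivity analysis.

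**Working it through.** **Inputs.** From Protocol Section 11.1: difference 5 points, SD 9.4, correlation 0.5 under compound symmetry, two time points, alpha 0.05, and 33 per group one-sided or 42 two-sided for 80% power. From the SAP: 30 per arm. The rate *p* of either event is not given; I assume 2% to 30%, equal in both arms.

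**Step 1: reproduce the protocol's figures.** The SD of the time average is 9.4 × √((1 + 0.5)/2) = 8.14. An 8-week ANCOVA has the same effective SD here, since 9.4 × √(1 − 0.5²) = 8.14. With n per arm, power = Φ(5 / (8.14 × √(2/n)) − z).

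- n = 33, one-sided (z = 1.645): 80.2%, matching the protocol's 0.80235.
- n = 42, two-sided (z = 1.960): 80.4%, matching the stated 42.

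Both reproduce, so the formula serves as a yardstick for the subset.

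**Step 2: all 60 patients.** With n = 30 per arm, power is 76.9% one-sided and 66.2% two-sided.

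**Step 3: the sentence as written.** Patients kept = 60*p*, or 30*p* per arm if balanced. The standard error grows by √(60/(60*p*)). The chance that at least one arm keeps fewer than two patients is 1 − (1 − B)², where B is the binomial probability of 0 or 1 events among 30.

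| Assumed rate | Kept of 60 | SE inflation | Two-sided power | Chance an arm has fewer than 2 |
|---|---|---|---|---|
| 2% | 1.2 | 7.1 | 5.2% | 98.5% |
| 5% | 3 | 4.5 | 7.7% | 80% |
| 10% | 6 | 3.2 | 11.4% | 33% |
| 15% | 9 | 2.6 | 14.9% | 9% |
| 20% | 12 | 2.2 | 18.5% | 2% |
| 30% | 18 | 1.8 | 25.6% | under 1% |

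The normal approximation flatters such small groups. With a t distribution, two-sided power is 8.6% at 3 per arm, 16.0% at 6 and 23.1% at 9. At the lowest rates the power figure is notional, because the comparison often could not be run.

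**Step 4: the reverse wording (exclude those *with* an event).** Patients kept = 60(1 − *p*).

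| Assumed rate | Kept of 60 | Power, one-sided | Power, two-sided |
|---|---|---|---|
| 5% | 57 | 75.0% | 64.0% |
| 10% | 54 | 73.0% | 61.7% |
| 20% | 48 | 68.5% | 56.7% |

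Precision is barely touched at low rates. What remains is selection. Protocol Section 2.2 sets out to test an antidepressant effect, so treatment may plausibly change the frequency of either event. YMRS is a secondary outcome in the SAP, and Protocol Section 9.4.4 describes it as rating core manic symptoms; removing switchers therefore partly selects on an outcome being compared. With no time window, an event reported on the day 84 call could also decide who enters a day 56 comparison.

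**Step 5: where the rule applies.** The ANCOVA, the alternative ANOVA and the mixed model (SAP, Primary analysis for efficacy) carry no such exclusion. Nor do the logistic model and the repeated-measures models (SAP, Secondary analyses related to efficacy), or the incidence comparison earlier in the Adverse Events section.

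**The case against.** The best reply is that this is a one-word slip in a minor analysis. The sentence before it says the events "will be examined thoroughly for impact on primary and secondary outcome measures", which fits repeating the comparison without the affected patients. Under that reading power hardly falls, nothing in the SAP makes the analysis confirmatory, and the literal version would be so plainly uninformative that it would probably mislead nobody.

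Much of this stands. A slip is the likeliest explanation, and the consequence is confined to one supplementary analysis. But a SAP is carried out as written, the two readings keep opposite sets of patients, and the likely intended version still conditions on a post-randomisation event without saying so.

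A reader might infer three stronger things that the documents do not support:

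- *That the trial's efficacy comparison would be run in a few patients.* It would not; the rule appears in none of the primary or secondary efficacy models.
- *That safety reporting is compromised.* The adverse-event table and the between-group comparison of each event type have no exclusion.
- *That the retained number is known to be a handful.* No rate is given for either event. The earlier 7-week trial in Protocol Section 9.3 lists serious suicidality events by arm without denominators, so it yields no rate. The entry criteria suggest low rates, but at 30% the subset would be 18 patients.

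**Conclusion.** The point holds for one sentence and one supplementary analysis. As written, the rule compares arms only among patients who had suicidality or a manic/hypomanic switch. The conclusion that this would be uninformative does not depend on where in the assumed 2–30% range the rate falls: even at the top, two-sided power is well under half that of the full sample. The figures assume equal rates, balanced retained arms and the protocol's own SD and correlation, and they count either event as qualifying; requiring both would leave fewer patients. The 5-point verbal learning difference is only a yardstick, since the sentence does not name the outcome to be compared.

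If 'with' was intended, the defect is smaller: an unlabelled, undefined selection after randomisation, whose bias cannot be sized from the documents. The wording should be corrected before unblinding. It gives no reason to doubt the planned efficacy models or the adverse-event incidence comparison.

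**What to change.** Replace the closing sentence of the SAP's Adverse Events section with:

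> Group differences on primary and secondary outcomes are assessed in all randomised patients. As a descriptive sensitivity analysis, the comparison is repeated excluding patients WITH suicidal ideation/behaviour or switch to mania/hypomania (either event, with onset after randomisation and up to the week 8 assessment). The number excluded is shown by arm, and the result is interpreted as conditional on a post-randomisation event.

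The SAP should also state how each event is identified from the data already collected, so that the excluded set can be fixed before unblinding.

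Cost: one replaced sentence and a short definition in the SAP. No new data, visits or sample size are needed, and no other analysis changes.
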